### **3.10 Nurses**

#### **3.10.1 Questionnaire II**

Questionnaire II consisted of two sections: Section A comprised the demographic characteristics of the nurses and Section B included three (3) main subscales for nurses' personal beliefs related to KC implementation in Parts I, II and III. There were 56 items. (see Appendix H for further information).

##### ***a) Section A: Demographic Characteristics***

Section A data were collected based on the demographic characteristics of the nurses in UMMC's NICU. All eight (8) variables were formatted to gather the baseline data and fulfill the study objectives. The variables included in this study were: age, race, marital status, working experience (RN), working experience in NICU, neonatal nursing certification, KC practice in NICU, and KC training experience. The rationale for measuring such data was to determine whether the selected variables had an effect on the perception, knowledge, and practices of the study participants in relation to KC.

##### ***b) Section B: Kangaroo Care Questionnaire (KCQ)***

In section B, the researchers used the KCQs tool developed by Arthur J. Angler & Eileen Brumbaugh., Ludington-Hoe., et al. (2013) for nurses. The questionnaire was adopted and slightly modified according to the Malaysian context; permission to standardize the questionnaire was granted by the owners of the tool themselves via email. The tool was selected to evaluate the effectiveness of KC practice in the Malaysian setting. The KCQs

were chosen in comparison to other scales, due to their simplicity and excellent reliability and validity. This scale is well known and has previously been used nationally by the formulator of the KCQs and other researchers. Other than that, according to the author's emailed communication the tool has been used with perinatal nurses from the north eastern United States and National Association of Neonatal Nurses (NANN) with an initial data reliability of 0.79 – 0.90 for each of the parts. The Cronbach's alpha is similar to our study range of between 0.78 – 0.95 for mothers and 0.79 – 0.90 for nurses. Only 56 items were used for the quantitative data for this study, consisting of three main parts that measured personal beliefs regarding perception, knowledge, and practices (monitoring device support) in relation to KC implementation. In addition, seven (7) staff nurses, each of whom had at least eight years of neonatal nursing experience, reviewed and updated the KCQs for clarification and consistency (Ludington-Hoe et al., 2001).

***a) Part I: Nurses' Perception of Kangaroo Care***

Part I assessed nurses' perception of KC related to their personal beliefs and the experiences that they had in the NICU. All twenty-five (25) items were adapted from the original KCQ tool developed by Arthur J. Angler & Eileen Brumbaugh, Ludington-Hoe et al. (2013), with slight modifications to meet the objectives of the study. A 5-point Likert response format was adopted. Descriptors were: strongly disagree (1) as the lowest score, followed by disagree (2), neither agree nor disagree (3), agree (4) and strongly agree (5); descriptor 5 was the highest score. With reference to the descriptors, the closer the score was to 5, the greater the appropriateness of the item. The items were positively and negatively worded (Appendix G). Positive items answered as 'strongly agree' or 'agree' were considered correct and if answered as 'strongly disagree', 'disagree' and 'neither agree nor disagree' were considered incorrect. The negative items were reversely rated. Out of 25 items there were 15 positive statements, which were (1,2,8,9,10,13,15,16,17,18,20,21,22,24,25), and 10 negative

statements, which were (3,4,5,6,7,11,12,14,19,23). The perception scores were converted into mean scores and then categorized into two groups. Mean scores of  $M=2.77$  and below indicated a high perception of KC, while mean scores above  $M=2.77$  indicated a low perception related to KC implementation. Therefore, mean scores of above 2.77 indicated less experience of KC with preterm infants in the NICU.

***b) Part II: Nurses' Knowledge of Kangaroo care***

The Part II questionnaire was on nurses' knowledge, determined by 20 true-false items to assess nurses' knowledge pertaining to initiation of KC with preterm infants in the NICU setting. The items were adopted from the KCQ tool developed by Arthur J. Angler & Eileen Brumbaugh, Ludington-Hoe et al. (2013). Nurses had to grade their level of knowledge according to 'not sure' (1), 'false' (2) and 'true' (3). These items were selected because they contained sufficient information to evaluate or report on the KC-related knowledge of mothers and infants. The items were worded in a positive and negative way. Positive items answered as 'true' were considered correct and if answered 'false' or 'don't know' were considered incorrect. The negative items were reversely rated. Out of 20 items there were 11 positive statements, which were (4,6,7,8,9,10,13,14,15,18,19), and nine negative statements, which were (1,2,3,5,11,12,16,17,20). The scores for knowledge were converted into mean scores, and then classified into two parts. Higher mean scores of  $M=2.34$  and above indicated good knowledge, while mean scores below  $M=2.34$  indicated poor knowledge and experiences in relation to KC in the NICU.

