***b) Part II: Mother's Knowledge on Kangaroo Care***

Part II of the mother's knowledge questionnaire was adapted from the original KCQs tool developed by Arthur J. Angler, & Eileen Brumbaugh, Ludington-Hoe, et al. (2013) with slight modifications so as to be relevant and meet the objectives of the mothers' outcomes. There were similar knowledge questionnaires for the mothers and nurses regarding their ability to implement KC. Mothers were requested to circle a number and indicate their opinion on their knowledge of KC. The scoring was from not sure (1) to false (2) and true (3). The items were worded in both positive and negative terms (Table 3.3). Positive items answered with 'true' were considered correct and incorrect if they were answered 'false' or 'not sure'. Out of 11 items, there were six positive statements, which were (1,2,4,6,7,8), and five negative statements, which were (1,2,3,5,11). A higher score indicated a higher level of knowledge with reference to the descriptors. Higher mean scores of  $M=2.03$  and above-indicated mothers had a good level of knowledge regarding KC, while lower mean scores below  $M=2.03$  indicated a poor level of knowledge on KC.

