### **3.19.4 Reliability**

The reliability of the instrument was measured by its stability and equivalence. The reliability of the content and construction of the questionnaire in this study were tested during the pilot study. A pilot study was conducted on 30 mothers and 50 nurses to test the reliability for the total population. The sample of mothers was collected from respondents in the NICU at UMMC. The same set of questionnaires was used twice to assess perception, knowledge, perceived barriers and stress. Cronbach's alpha ( $\alpha$ ) was 0.813 for the perception subscale; 0.873 for the perceived barriers subscale; 0.951 for the sub-scale of stress. Furthermore, KR20 for the knowledge subscale was 0.785. The researchers assumed that the translated KCQs and PSS: NICU: P&R instruments were reliable during the internal consistency test. The Content Validity Index of the KCQs Malay version was 0.95, which was considered acceptable. Reliability ensures an instrument has consistent and dependable scores (Creswell, 2005). In reliability values, the indicators to be measured are Cronbach alpha ( $\alpha$ ) value, person reliability value, individual measurement, and relevant responses (Azrilah Abdul Aziz, 2010). Fraenkel and Wallen (1996) reported that the reliability of an item would be accepted if the alpha is between 0.70 and 0.99, while Kubiszyn and Borich (2000) indicated that an  $\alpha$  value within the range between 0.80 and 0.90 should be acceptable.

The data was analyzed using descriptive statistics, The frequency for continuous data, general linear model, and repeated measure was used for categorical data and mean (standard deviation). The statistical analysis was carried out using version 23.0 of the SPSS. The participants were assured of confidentiality and that the safety of the mothers and premature infants was maintained. Care was taken that there was no exploitation of human rights, humanity or discrimination of any type. Ethical clearance from the teaching hospital's ethical committee was also granted before the study began.

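### The knowledge score averages nominal response codes, so it does not rank nurses or mothers by how many items they answer correctly

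*Combined protocol and SAP*

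**What the plan says.** **Nurses (section 3.10.1, Part II).** The codes are given as: "Nurses had to grade their level of knowledge according to 'not sure' (1), 'false' (2) and 'true' (3". The form in Appendix H prints the same codes. The items are split as follows: "Out of 20 items there were 11 positive statements, which were (4,6,7,8,9,10,13,14,15,18,19"; and "nine negative statements, which were (1,2,3,5,11,12,16,17,20". The marking rule is: "Positive items answered as 'true' were considered correct and if answered 'false' or 'don't know' were considered incorrect". The next sentence reads: "The negative items were reversely rated". No mapping for the reversal is given. Then: "The scores for knowledge were converted into mean scores, and then classified into two parts", with a mean of 2.34 or above labelled good and below it poor.

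**Mothers (section 3.8.1, Part II).** The 11 items use the same three codes. *True* on a positive item is correct, and *false* or *not sure* is incorrect. No reversal is stated for this scale. The positive items are listed as six, "which were (1,2,4,6,7,8), and five negative statements, which were (1,2,3,5,11". The cut-off is 2.03.

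**Use of the score.** Hypotheses H1 and H3 (section 1.6) name knowledge for mothers and nurses respectively, and Table 3.4 makes the mean score the analysed variable for both. Section 3.19.4 reports that "KR20 for the knowledge subscale was 0.785" for the mothers' instrument. Table 3.6, whose title names both Cronbach's alpha and KR20, gives 0.793 for the nurses' knowledge items.

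**The concern.** An average of 1, 2 and 3 is meaningful only if the codes are ordered by knowledge. Here they are not: *not sure* sits at one end of the code range and the two definite answers fill the rest. On a positive item that puts a wrong answer above an admission of not knowing. On a negative item, turning the scale round moves *not sure* from the bottom to the top, above the correct answer.

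The text also mixes two scoring systems. Right/wrong marking and KR20 both belong to 0/1 items, while cut-offs of 2.34 and 2.03 belong to the 1–3 codes. The reliability figure may therefore describe a different score from the one analysed.

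At stake is whether the comparisons on knowledge, before and after for nurses and between groups for mothers, measure a gain in knowledge at all, and whether the good/poor classification is right.

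**Working it through.** **Inputs.** Codes: *not sure* 1, *false* 2, *true* 3 (section 3.10.1, Part II; Appendix H). There are 11 positive and 9 negative items, and together the printed lists use each of items 1 to 20 once. Cut-off: 2.34. The calculation takes the printed lists as the key, so the correct answer is *true* on the 11 and *false* on the 9.

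**The plan's own figure.** No derivation of 2.34 is given, so it cannot be reproduced. Since 2.34 × 20 = 46.8, it is not an attainable mean for one nurse answering all items. It exceeds 1, so the averaged score cannot be made of 0/1 marks. The same holds for the mothers' 2.03.

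**Formula.** Mean = (11 × positive code + 9 × negative code) / 20. Because the reversal is not written out, three treatments of negative items are shown:

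- Usual reversal, 4 − x: *not sure* 3, *false* 2, *true* 1.
- No reversal: *not sure* 1, *false* 2, *true* 3.
- True and false swapped only: *not sure* 1, *true* 2, *false* 3.

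| Nurse's answers | Correct | 4 − x | No reversal | Swap |
|---|---|---|---|---|
| All correct | 20 | 2.55 | 2.55 | 3.00 |
| Positives correct, negatives *not sure* | 11 | 3.00 | 2.10 | 2.10 |
| Positives correct, negatives wrong | 11 | 2.10 | 3.00 | 2.55 |
| Positives *not sure*, negatives correct | 9 | 1.45 | 1.45 | 1.90 |
| Positives *false*, negatives *not sure* | 0 | 2.45 | 1.55 | 1.55 |
| All wrong | 0 | 1.55 | 2.45 | 2.00 |
| All *not sure* | 0 | 1.90 | 1.00 | 1.00 |

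For example, under 4 − x, all correct is (33 + 18)/20 = 2.55; positives correct with negatives *not sure* is (33 + 27)/20 = 3.00; positives *false* with negatives *not sure* is (22 + 27)/20 = 2.45.

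**Change per item under 4 − x when a nurse learns the answer.**

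- Positive, *not sure* to *true*: +2.
- Positive, *false* to *true*: +1.
- Negative, *true* to *false*: +1.
- Negative, *not sure* to *false*: −1.

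The largest loss is 9 × 1/20 = 0.45. From all *not sure* to all correct the gain is 2.55 − 1.90 = 0.65. If all learning starts from *not sure*, with p positives and n negatives learned, the total changes by 2p − n. It falls only when n is more than twice p.

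**Classification under 4 − x.** Five positives right, six *not sure* and all nine negatives *not sure* gives (15 + 6 + 27)/20 = 2.40: good, with 5 correct. Eight positives right, three *not sure* and all nine negatives right gives (24 + 3 + 18)/20 = 2.25: poor, with 17 correct.

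**Positive items under any treatment.** A wrong *false* scores 2 and *not sure* scores 1, although both are called incorrect.

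**Mothers.** With no reversal, a wrong *true* on a negative item scores 3 and a correct *false* scores 2. Answering *true* to every item gives 33/11 = 3.00, the maximum, whatever the key. The two lists contain 6 + 5 = 11 entries but only nine distinct items: 1 and 2 are in both, 9 and 10 in neither. A total per number of correct answers therefore cannot be computed.

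**The key against the study's own materials.**

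- Nurses' item 1, that infants seem content during kangaroo care, is listed as negative.
- Nurses' item 3, on infants under phototherapy taking part, is listed as negative, while the Appendix P slides place phototherapy under indications.
- Mothers' item 5, on better breathing patterns, is listed as negative, while the mothers' teaching module says that kangaroo care controls respiration.
- Mothers' item 6, that kangaroo care is contraindicated in premature infants, is listed as positive.

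These places must be reconciled.

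**The case against.** The strongest reply is that the 4 − x mapping is inferred. The sentence on reversal follows directly on the rule for correct and incorrect answers, so it could mean only that *false* becomes the right answer on negative items. A swap of true and false fits the 1–3 codes, allows a cut-off such as 2.34, and removes the loss. This stands: the loss is conditional on the usual meaning of reverse rating. But the plan never states a swap, and a swap does not repair the score. All wrong scores 2.00 and all *not sure* 1.00, with no correct answer in either. Reversing the marking rule literally would also credit *don't know* on negative items.

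A reader might infer that *not sure* earns the top mark generally, or that teaching lowers the score. The documents do not support that. Only one of the four learning moves loses points, and the full 0.45 needs a nurse who already has all 11 positives right and is unsure of all nine negatives.

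A reader might also extend that loss to mothers. No reversal is stated for them, so *not sure* is always lowest and moving to the right answer gains 1 or 2. Their scale fails in a different way.

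It is also fair that the sample size rests on weight gain, not knowledge, and that the polarity lists are themselves doubtful, so 2.55 and 0.45 are scores against the printed key, not of true knowledge.

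**Conclusion.** The point holds in this form. None of the three treatments makes the averaged codes follow the number of correct answers, in either population.

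For nurses, if reversal means 4 − x and the printed lists are the key, learning a negative item from *not sure* loses 1 point, at most 0.45 on the 20-item mean, and someone with nothing right can be classed as having good knowledge at 2.45. The measured effect can be diluted or turned negative depending on the mix of responses. It need not be, since other moves gain and the full move from *not sure* to correct gains 0.65.

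The ranking of a wrong *false* above *not sure* on positive items needs no assumption about reversal. For mothers, the ranking of a wrong *true* above a correct *false* on negative items follows from the text as written, and the item lists cannot be applied as printed.

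Knowledge is named in two of the three hypotheses, so this should be corrected before those results are interpreted. It does not touch weight gain, length of stay or breastfeeding.

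**What to change.** 1. Write one answer key for each questionnaire, listing every item once, and settle it without reference to the responses. Reconcile it with the forms in Appendices E(a) and H and with the teaching materials, starting with nurses' items 1 and 3 and mothers' items 1, 2, 5, 6, 9 and 10.
2. Score each item 1 if the answer matches the key and 0 otherwise, with *not sure* counted as 0.
3. Analyse number or percent correct. On 0/1 marks, all *not sure* is 0.00, the 11 positives alone correct is 0.55, and all correct is 1.00, so the order is right.
4. Drop the 2.34 and 2.03 cut-offs, which have no meaning on the new scale.
5. State whether the reported KR20 values came from 0/1 marks under the same key, and recompute them if not.

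The cost is recoding item responses already collected; no new data are needed. Scores will no longer be on the 1–3 scale, so any knowledge results or classes already produced must be rerun.

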***c) Part III: Nurses' Practice of Kangaroo Care***

Part III related to nurses' satisfaction in practicing KC with premature infants with various types of conditions or treatment in the NICU. The eleven (11) items were formulated by adopting the subscale for practices with monitoring devices. The items were adapted from the original KCQ tool developed by Arthur J. Angler & Eileen Brumbaugh, Ludington-Hoe et al. (2013) with minor changes to meet the study objectives and specifications. Nurses were requested to circle a number to indicate their confidence level and skills based on a 5-point Likert scale. The descriptors were: very uncomfortable (1), somewhat uncomfortable (2), neither comfortable (3), somewhat comfortable (4) and very comfortable (5). Out of 11 items, there were four positive statements, which were (1,2,5,6), and seven negative statements, which were (3,4,7,8,9,10,11) Table 3.11. The items were positively and negatively worded. Practice scores for the monitoring device were converted to mean scores and then divided into two categories. Mean scores of  $M= 2.26$  and below indicated a high level of confidence and skills in initiating KC, while mean scores above  $M=2.26$  indicated a low level of confidence and skills in initiating KC with monitoring devices in the NICU.

### **3.11 Kangaroo Care Educational Programme**

Biswas, Malpani & Ekka, (2016) concluded that nurses with no formal training of KC were often limited in their KC practice. These components were also intended to improve the knowledge and skills of nurses in the appraisal of mother-infant dyads to help them achieve KC and to promote breastfeeding as the primary and secondary outcomes. Gayathri, Sampada, Hiral, Manisha, Silvi, & Yashvanthi, (2016) suggested that a structured teaching program (STP) would enhance KC knowledge among postnatal mothers with low birth weight infants. Subsequently, the structured kangaroo care education program (KC-EP) for mothers and nurses was conducted to enhance knowledge and skills related to KC's benefits and included a theory and a practical session.

This program was based on Knowles' adult learning theory, with the Andragogy model's five assumptions. According to Rogers (2001), a single motto-learner abides by the effective teaching of adult students. The program sought to acquire the cognitive (intellectual), affective (values, emotions, and feelings) and psychomotor (motor skills) competence that reflects the imperative of enhancing nursing education skills, knowledge, and attitudes (Anderson & Krathwohl, 2001; Huitt, 1992; Bloom et al., 1956). Munn stated that learning is more or less a permanent change in behavior as a result of observation, training and action, either in person or by teaching (Kahayon & Aquino, 1995). The informed consent, verbal and written, of all the study subjects was taken before the study started.

***i) Structured Kangaroo Care Educational Program for Mothers (KC-EP)***

The KC-EP for mothers is a special program designed to help preterm infant mothers admitted to the NICU share evidence of the benefits of KC and show them how they can perform KC. There are plenty of online reading and video resources available: blogs, books, magazines, newsletters or newspaper articles, on issues faced by preterm infant mothers admitted to the NICU and how they can reduce maternal stress during separation and improve their neonatal care capabilities related to the NICU. Most of the available materials are general and do not address specific guidelines and practice protocols for performing kangaroo care.

Therefore, a formal content module for mother-infant dyads was developed for the KC-EP. The KC-EP focused on the psychological and physical aspects related to the preparation for and implementation of the KC procedure (before, during, and after). Subsequently, proper handwashing techniques (before and after touching the premature infant) and KCPR booklet documentation were implemented. On the other hand, for interpersonal communication or interaction between mothers and neonatal nurses in the NICU and good relations were established. In addition, mothers were also encouraged to participate in some tasks that were

usually carried out by current ward staff for their premature infants in the NICU, i.e. changing diapers, feeding tube or cup feeding and breastfeeding. In other words, for mothers, the KC-EP was more formal, simplified and based on contextualizing the needs of the regional culture in Malaysia. The positive point is that these short notes, such as flipcharts and leaflets in both languages, could be used to illustrate points for the premature infant mothers and as a quick reference for the neonatal nurses.

This program (KC-EP) had the general objective of ensuring the intervention with the mother-infant dyads was effective and possibly at no cost. The specific aims were to:

- a. Provide mothers with educational information related to KC to ensure the quality of premature infant care at the hospital and after returning home.
- b. Assist mothers in situations, and with facilities, and routine care in the NICU during their premature infant's hospitalization in the NICU.
- c. Develop interpersonal communication and interaction between mothers and neonatal nurses.
- d. Support mothers regarding the psychological aspects of their premature infants.
- e. Advocate for mothers to perform kangaroo care at least 1 hour a day and accumulate to 4 to 5 hours a week until 3 months of age. Evidenced by Kangaroo Care practice.

### **i) Contents Module Theory (30 minutes)**

#### **1. Introduction : Kangaroo care .**

Kangaroo care (KC) started in Bogota, Colombia approximately 30 years ago. According to WHO ( 2014) KC is in Africa - Benin, Burkina Faso, Ethiopia, Mali and Malawi ; in Asia - India, Indonesia and the Philippines (Recent study, 1990, 2012); and in Europe - France, Denmark, Belgium,

Netherlands, Italy, Spain, the United Kingdom and Sweden, (Spanish research survey, 2013). Evidence suggests that visiting, holding, talking and skin-to-skin contact are linked to positive outcomes for infants and parents during and after hospitalization (Feeley, Genest, Niela-Vilin, Charbonneau, & Axelin, 2016)

KC improves cerebral blood flow (CBF), thus influencing the structure and encouraging the development of the brain of the premature infant. (Korraa, El Nagger, Mohamed, & Helmy, 2014).

KC can be used to promote emotional bonding between mothers and infants and to regulate a premature infant's physiological functions, and is perhaps one of the NICU's most effective nursing interventions for premature infants and their mothers (Cho et al., 2016).

Evidenced: Doctors and nurses have been trained on KC theory and skills procedure in NICU, UMMC.

